### **5.1.2 Clinical Care**

It is standard clinical practice that most patients receive a central venous (vena jugularis, incidentally vena subclavia) and an arterial (arteria radialis) catheter when admitted to the intensive care unit. Patients with anaemia having an arterial catheter will be included in the study. During the pilot phase of the study, patients did not need to have a central venous catheter since the pilot study is about the feasibility of the mitoPO2 measurement and not the outcomes. Blood samples will be drawn from these catheters. Patient management will take place according to usual care. When patients meet the inclusion criteria, an ALA-patch will be placed. After at least four hours PpIX induction, the cutaneous mitoPO2 sensor will be placed to make the first measurements. Transfusion will be given in an one hour. The clinician can deviate from this time frame if the condition of the patient doesn't permit a 1 hour lead time. After red blood cell transfusion, measurements of the mitoPO2 will be made at predefined moments.

## **5.2 Withdrawal of individual subjects**

Subjects can leave the study at any time for any reason if they wish to do so without any consequences. The investigator can decide to withdraw a subject from the study for urgent medical reasons. These subjects will not be subjected to follow-up.

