### **5.3.2 Gathering and handling of clinical data**

While waiting for the induction of PpIX after placement of the ALA patch, data will be gathered. Appendix 2 shows an overview of the data collection. First of all, demographic data will be collected: age in years, gender, weight, height, Body Mass Index, allergies, medication use, comorbidities (acute and chronic), and reason of ICU admission. Also, pulmonary function, renal function, APACHE-II and APACHE-IV will be assessed. The demographic data can be obtained from the hospital's electronic patient dossier system (EPD).

---

Clinical data will be assessed as well, which are: heart frequency (HF), blood pressure (BP), central venous pressure (CVP), and peripheral oxygen saturation (SpO2). These will be assessed at the same time points as the mitoPO2 measurements. Daily the Glasgow coma scale, 24h-urine production, electrocardiogram (ECG), RIFLE classification, SOFA score, RASS, and ICDSC score will be collected. These measurements are already done, as part of the daily intensive care management, and will be collected using the EPD. Other data collected from the EPD are: vasopressor use, inotropic therapy, mechanical ventilation duration and settings, P/F ratio, Aa gradient, need for continuous renal replacement therapy (CRRT) and, if applicable, duration of CRRT. Also, cardiac index will be measured before and after red cell transfusion with the help of a non-invasive Vigilance II. This measurement isn't part of standard care.

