### 5.3.3 Blood samples

In addition to clinical characteristics and mitoPO2, we will measure Hb, haematocrit, arterial oxygen saturation (SaO2) and oxygen tension (PaO2), central venous oxygen saturation (ScvO2) if applicable and oxygen tension (PvO2) if applicable, and lactate in arterial and venous blood (if applicable) samples taken at the predefined moments before and after red cell transfusions. The collected blood will be immediately transported via the regular transport tubing system to the CKCL and CKHL for these analyses after being labelled with the unique subject number. Other measurements that will be done, in venous blood are: troponin, creatinine kinase, and creatinine. Urine will be collected for 24 hours on the day of transfusion itself and the day after, to calculate the glomerular filtration rate (GFR). Blood samples are already taken multiple times during a 24-h ICU stay, as part of a normal intensive care management. For this study troponin is not part of the daily routing of the ICU. Therefore, determination of troponin will be added. Appendix 2 gives an overview of measurements part of standard care, and which of those measurements are part of the study.

Information regarding ICU stay, hospital stay and mortality (ICU and hospital) will be available in and collected from the EPD. The follow up period will be three months. All data will be entered after validation in a study database for subsequent tabulation and statistical analysis. The data will be handled confidentially and anonymously. Patients re-admitted to the ICU and already participating in this study will only be followed according to the study protocol. Thus re-admitted patients will not be included for the second time.

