### 5.3.4 Sample handling and Measurements:

Samples will be collected from

- central venous catheter (if applicable)
- arterial catheter

In order to make comparisons between different compartments of the body, blood samples (arterial, central venous) and cutaneous samples will be collected at predefined moments.

These moments during the pilot study are:

- Before transfusion (=T0)
- At the end of each transfusion (=T1)
- 30 minutes after T1 (=T2)
- 60 minutes after T1 (=T3)
- 180 minutes after T1 (=T4)
- 24 hours after T1 (=T5)

With the help of the pilot study, an overview of the measurements and parameters were made.

With the help of this overview, decisions were made regarding the number of measurement moments (e.g. no need for measurement 15 minutes after red cell transfusion). Details about which parameters are determined at each time point during this pilot study are described in appendix 2. For the laboratorial measurements a total of 42ml of blood will be taken (10ml at T0 and T5, 4ml at T1 and T2, 6ml at T3 and 7.5ml at T4). As can be seen in appendix 2, most of the measurements are part of standard care which minimalizes the burden for the patient.

Figure3: Measurement MitoPO2 with the Comet

Analysis of red blood cell transfusion on the intensive care unit at LUMC showed 69% of transfusions occurred during daytime (between 8.00hr and 18hr). The remaining transfusions were evenly distributed in the evening and night time. Since transfusions outside the normal daytime are mostly because of urgent medical reasons, no measurements will be done in the evening or night.

Besides time of transfusion, analysis of previous ICU data showed that the mean duration elapsing between the decision of a non-emergency red cell transfusion and the start of the transfusion is 2-3 hours. Thus, maximum of 2 hours delay for start of transfusion during this study is achieved. However, at no time red cell transfusion will be delayed if the patient is clinically in need of a transfusion in order to have enough time to induce PpIX. To ensure this, the clinician responsible for the patient, and not the researcher, has the final decision in the timing of the red cell transfusion. The delay of transfusion will be recorded to gain an insight in delay of transfusion.

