### 5.4.2 Secondary outcomes

Secondary study outcomes include:

- Value of mitoPO2 measurements in predicting (ischemic) organ damage. The following parameters for organ damage (that are routinely collected) will be assessed: lung (pO2/FiO2 ratio), heart (troponin, CK, an ECG, CI), renal (creatinine, urine production, glomerular filtration rate, RIFLE classification), brain (delirium, RASS) and SOFA score. More details about the timing of these parameters are given in appendix 2.
- Microcirculatory value of mitoPO2
- Duration of mechanical ventilation
- Need for renal replacements therapy
- Length of ICU stay
- Length of stay in hospital
- Hospital mortality
- ICU mortality
- 90-day mortality
- Assessment the safety of mitoPO2 measurements
  - Delay of transfusion because of mitoPO2 measurements
  - Adverse and serious adverse events of the mitoPO2 measurements

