### 6.2 Statistical methods to be employed

Absolute differences and 95% confidence intervals will be calculated. In addition to the univariate comparisons we will also calculate the differences for each of the parameters independent of the other parameters using multivariate models. In addition, we will perform similar analyses in subgroups of Hb and reason of admission (classified by APACHE IV) to assess whether the observed effect of transfusion on the parameters differs between the groups. We will also examine whether the decrease of the mitoPO2 precedes changes of other measures of oxygenation.

For the dichotomous outcomes logistic regression will be applied. For time-to event outcomes the univariable analysis will be performed using the Kaplan-Meier method, the multivariable analyses the Cox proportional hazard model. To determine the discriminative power of the model, the ROC curve with the c-statistic.  $P < 0.05$  will be considered statistically significant for the primary outcome measure. The statistical analysis will be conducted using the SPSS (Statistical Package for the Social Sciences) statistical package, release 23.0 (SPSS Inc., Chicago, IL) and STATA.

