### 7.3 Adverse events (AEs)

Adverse events are defined as any undesirable experience occurring to a subject during the study, whether or not considered related to the investigational product. All adverse events reported spontaneously by the subject or observed by the investigator or his staff will be recorded.

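### Section 5.2 ends follow-up for patients the investigator withdraws for urgent medical reasons, although they have not refused, and is not reconciled with AE follow-up in section 7.7

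*Protocol*

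**What the plan says.** Section 5.2 gives two ways out of the study. Subjects may leave whenever they wish. Separately: "The investigator can decide to withdraw a subject from the study for urgent medical reasons. These subjects will not be subjected to follow-up". Whether the last sentence covers one route or both, it includes patients withdrawn by the investigator.

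Section 5.3.3 states "The follow up period will be three months", directly after saying where the outcomes come from: "Information regarding ICU stay, hospital stay and mortality (ICU and hospital) will be available in and collected from the EPD". For the daily organ scores, section 5.3.2 says "These measurements are already done, as part of the daily intensive care management, and will be collected using the EPD"; it takes ventilation and CRRT data from the same record.

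Section 5.4.2 lists the secondary outcomes: organ damage, ventilation, renal replacement, ICU and hospital stay, ICU and hospital mortality, "90-day mortality", and AEs and SAEs of the measurement. Section 6.2 plans their analysis: "For time-to event outcomes the univariable analysis will be performed using the Kaplan-Meier method, the multivariable analyses the Cox proportional hazard model".

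Section 7.7 has all AEs followed until resolved or stable, and SAEs reported to the end of the study. It makes no exception for withdrawn subjects.

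Sections 8.2, 8.3 and 10(g) deal with data after refusal, retraction or missing written consent. None of them deals with withdrawal by the investigator.

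**The concern.** Stopping data collection after a refusal respects the patient's choice. A patient withdrawn by the investigator has made no such choice, so there is no consent reason to stop extracting routine data.

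The patients concerned are those whose condition turned urgent. That plausibly goes with death, organ damage, ventilation and renal replacement, which are the outcomes that would go uncollected. Missingness in the secondary outcomes is then likely related to the outcome itself, and censoring at withdrawal in a Kaplan-Meier or Cox analysis is likely informative. The 10% drop-out allowance in section 6.1 replaces numbers but does not correct selection.

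There is also a safety side. Sections 5.2 and 7.7 give different instructions for an AE that is open when the patient is withdrawn, and neither refers to the other.

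**Working it through.** **1. What follow-up means here.** Section 5.2 does not define it. The only stated follow-up period is the three months of section 5.3.3, given next to the collection of stay and mortality. Read together, no follow-up means that those outcomes stop at withdrawal. Sections 8.2, 8.3 and 10(g) do not undo this, because they apply only to refusal, retraction or missing consent.

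**2. The overlap with section 7.7.** Section 7.3 limits the definition: "Adverse events are defined as any undesirable experience occurring to a subject during the study". Section 7.4 takes SAEs due to underlying disease, and SAEs expected during the ICU course, out of reporting. What remains in clear conflict is an AE that began before withdrawal and is still open, plus any reportable SAE. The conflict is real but narrow.

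**3. How much of the observation is passive.** Inputs: at least 4 h patch induction (section 4), 1 h transfusion (section 5.1.2), last measurement T5 at 24 h after the end of transfusion (section 5.3.4).
- Active window: 4 + 1 + 24 = 29 h.
- Share of 90 days: 29 / (90 × 24) = 29 / 2160 = 1.3%.
- Remainder: 90 − 29/24 = 88.8 days.

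This counts 90 days from patch placement. Section 9.5 defines the end of the study from ICU admission; if day 90 is counted from there, time in the ICU before the patch shortens the remainder, so about 89 days is an upper bound. Only 90-day mortality spans it; the ICU outcomes accrue much sooner.

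**4. Bounds without any assumption about prognosis.** The plan's own figures are 189 subjects, raised to 209 for drop-out (section 6.1). The printed product 189 × 1.1 is 207.9; the gap from 209 does not matter here. With x of 209 outcomes uncollected, a binary proportion is open by x/209:

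| x | Width (percentage points) |
|---|---|
| 1 | 0.48 |
| 2 | 0.96 |
| 4 | 1.91 |
| 20 | 9.57 |

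The last row uses the whole drop-out allowance (209 − 189 = 20). It is a ceiling that assigns every drop-out to this cause.

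**5. Precision, as illustration.** Section 7.4 gives a national ICU mortality of 8.4%, for all ICU patients and not this cohort. Expected ICU deaths: 209 × 0.084 = 17.56. One uncollected death is 1/17.56 = 5.7% of events. With the variance of a log hazard ratio proportional to 1/events, losing d deaths multiplies the standard error by √(1/(1 − d/17.56)): 1.030 for d = 1, 1.062 for d = 2, 1.098 for d = 3. This assumes that the lost deaths had mitoPO2 values.

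**6. Selection, as illustration.** Let p = 8.4% be the true mortality, w the share withdrawn and m the mortality among them. The complete-case estimate is (p − w·m)/(1 − w). The values of w and m are assumptions; the protocol gives neither.
- w = 2%, m = 20%: (0.084 − 0.004)/0.98 = 8.2%.
- w = 5%, m = 30%: (0.084 − 0.015)/0.95 = 7.3%.
- w = 10%, m = 50%: (0.084 − 0.050)/0.90 = 3.8%.
- m = 8.4%: no bias at any w, only fewer observed deaths.

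The bias in the associations with mitoPO2 cannot be quantified from the protocol.

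**The case against.** The strongest reply is that the harm depends on one reading of an undefined word. The phrasing of section 5.2 fits procedures imposed on a patient. Sections 5.3.2 and 5.3.3 describe record extraction without excepting withdrawn patients. Where the protocol wants collection to end, as in sections 8.2 and 8.3, it says so outright, and section 5.2 does not. On that view measurements stop and extraction goes on. Likewise, section 7.7 can be read as the specific safety rule that prevails over a general sentence. This softer reading is possible, but it is stated nowhere, and two centres could apply the sentence differently.

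The second reply is about size, and most of it stands. Emergency transfusions are excluded (section 3.2), the treating clinician controls transfusion timing (section 5.1.1), and a suspected skin lesion stops the measurements, not participation (section 10(j)). The group may be very small. Patients withdrawn before T0 have no mitoPO2 value and cannot inform its associations; for them only the descriptive outcomes are lost. That leaves about 25 h (1 + 24) between T0 and T5 as the main exposure.

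It is also fair that section 6.2 does not say which outcomes are time-to-event, so the censoring argument has no named target, and that the scope of consent for extraction after withdrawal cannot be judged without the consent form. The first point does not remove the loss of data; the second is a condition on the remedy.

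**Conclusion.** The concern holds. Section 5.2 states a rule; it is not a gap left for an analysis plan. Followed as written, it selectively loses secondary outcomes in patients who have not refused, and it leaves section 7.7 unreconciled for AEs open at withdrawal and for reportable SAEs.

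Severity is low to moderate. The conclusion rests on the natural reading of follow-up and on the plausible, untested assumption that urgent medical withdrawal is related to outcome. The number of patients affected is unknown. The primary endpoint is not targeted, the secondary aims are descriptive (section 2.2), and no figure in the protocol is wrong because of this point. The change is worth making because it is cheap and the loss cannot be repaired afterwards.

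**What to change.** Amend section 5.2 as follows.

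- Withdrawal by the investigator ends study-specific measurements only: mitoPO2, sublingual imaging, cardiac index and the additional study blood samples.
- Where written consent exists and has not been retracted, the routine-record outcomes (ICU and hospital stay, ICU and hospital mortality, ventilation, CRRT, organ function) and day-90 status are collected as for other subjects, and these patients stay in the secondary analyses. Check that the consent text covers this.
- AEs and SAEs of withdrawn subjects are handled under section 7.7, with a cross-reference in both sections.
- Sections 8.2, 8.3 and 10(g) continue to govern refusal, retraction and missing consent.

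The cost is a small amendment and a little more data extraction. Most of the items already come from the patient record. The protocol does not say how day-90 status after discharge is obtained, so that item takes the same effort as for any other subject. No measurement burden is added for the patient.

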## **5.3 Data collection**

### **5.3.1 MitoPO2 measurements**

MitoPO2 is measured at the skin at the predefined moments described in detail in the next paragraph. With each measurement, the circumstances of the measurement will be recorded in the log (e.g. skin temperature) to assess possible bias of measurements.

### **5.3.2 Gathering and handling of clinical data**

While waiting for the induction of PpIX after placement of the ALA patch, data will be gathered. Appendix 2 shows an overview of the data collection. First of all, demographic data will be collected: age in years, gender, weight, height, Body Mass Index, allergies, medication use, comorbidities (acute and chronic), and reason of ICU admission. Also, pulmonary function, renal function, APACHE-II and APACHE-IV will be assessed. The demographic data can be obtained from the hospital's electronic patient dossier system (EPD).

---

Clinical data will be assessed as well, which are: heart frequency (HF), blood pressure (BP), central venous pressure (CVP), and peripheral oxygen saturation (SpO2). These will be assessed at the same time points as the mitoPO2 measurements. Daily the Glasgow coma scale, 24h-urine production, electrocardiogram (ECG), RIFLE classification, SOFA score, RASS, and ICDSC score will be collected. These measurements are already done, as part of the daily intensive care management, and will be collected using the EPD. Other data collected from the EPD are: vasopressor use, inotropic therapy, mechanical ventilation duration and settings, P/F ratio, Aa gradient, need for continuous renal replacement therapy (CRRT) and, if applicable, duration of CRRT. Also, cardiac index will be measured before and after red cell transfusion with the help of a non-invasive Vigilance II. This measurement isn't part of standard care.

### 5.3.3 Blood samples

In addition to clinical characteristics and mitoPO2, we will measure Hb, haematocrit, arterial oxygen saturation (SaO2) and oxygen tension (PaO2), central venous oxygen saturation (ScvO2) if applicable and oxygen tension (PvO2) if applicable, and lactate in arterial and venous blood (if applicable) samples taken at the predefined moments before and after red cell transfusions. The collected blood will be immediately transported via the regular transport tubing system to the CKCL and CKHL for these analyses after being labelled with the unique subject number. Other measurements that will be done, in venous blood are: troponin, creatinine kinase, and creatinine. Urine will be collected for 24 hours on the day of transfusion itself and the day after, to calculate the glomerular filtration rate (GFR). Blood samples are already taken multiple times during a 24-h ICU stay, as part of a normal intensive care management. For this study troponin is not part of the daily routing of the ICU. Therefore, determination of troponin will be added. Appendix 2 gives an overview of measurements part of standard care, and which of those measurements are part of the study.

Information regarding ICU stay, hospital stay and mortality (ICU and hospital) will be available in and collected from the EPD. The follow up period will be three months. All data will be entered after validation in a study database for subsequent tabulation and statistical analysis. The data will be handled confidentially and anonymously. Patients re-admitted to the ICU and already participating in this study will only be followed according to the study protocol. Thus re-admitted patients will not be included for the second time.

### 5.3.4 Sample handling and Measurements:

Samples will be collected from

- central venous catheter (if applicable)
- arterial catheter

In order to make comparisons between different compartments of the body, blood samples (arterial, central venous) and cutaneous samples will be collected at predefined moments.

These moments during the pilot study are:

- Before transfusion (=T0)
- At the end of each transfusion (=T1)
- 30 minutes after T1 (=T2)
- 60 minutes after T1 (=T3)
- 180 minutes after T1 (=T4)
- 24 hours after T1 (=T5)

With the help of the pilot study, an overview of the measurements and parameters were made.

With the help of this overview, decisions were made regarding the number of measurement moments (e.g. no need for measurement 15 minutes after red cell transfusion). Details about which parameters are determined at each time point during this pilot study are described in appendix 2. For the laboratorial measurements a total of 42ml of blood will be taken (10ml at T0 and T5, 4ml at T1 and T2, 6ml at T3 and 7.5ml at T4). As can be seen in appendix 2, most of the measurements are part of standard care which minimalizes the burden for the patient.

Figure3: Measurement MitoPO2 with the Comet

Analysis of red blood cell transfusion on the intensive care unit at LUMC showed 69% of transfusions occurred during daytime (between 8.00hr and 18hr). The remaining transfusions were evenly distributed in the evening and night time. Since transfusions outside the normal daytime are mostly because of urgent medical reasons, no measurements will be done in the evening or night.

Besides time of transfusion, analysis of previous ICU data showed that the mean duration elapsing between the decision of a non-emergency red cell transfusion and the start of the transfusion is 2-3 hours. Thus, maximum of 2 hours delay for start of transfusion during this study is achieved. However, at no time red cell transfusion will be delayed if the patient is clinically in need of a transfusion in order to have enough time to induce PpIX. To ensure this, the clinician responsible for the patient, and not the researcher, has the final decision in the timing of the red cell transfusion. The delay of transfusion will be recorded to gain an insight in delay of transfusion.

